5. STUDY TREATMENT AND CONDUCT

5.1 Study Treatment

Supply, Packaging and Labelling of AZD4205

AZD4205 drug substance and drug product to be used for this clinical study are manufactured in accordance with Good Manufacturing Practice (GMP).

AZD4205 will be given orally once daily as capsule(s). Doses should be taken approximately 24 hours apart at the same time point each day. For the purpose of planning, each 3 week period (21 days) will be defined as a Cycle.

Capsules will be packed in HDPE bottles with child-resistant closures. One or more bottles of AZD4205 will be dispensed at each dispensing visit depending on the dose. Bottles will be dispensed to subjects in the Sponsor packing provided. The packaging includes bottles, caps and a label. Bottle tampers should not be broken prior to dispensing study drug to a patient.

Labels will be prepared in accordance with Good Manufacturing Practice and local regulatory guidelines. The labels will fulfil Good Manufacturing Practice requirements for labelling. Label text will be translated into local language.

The label will include the Name of the Sponsor, Protocol Number, For Clinical trial use only and/or any other market specific requirements.

AZD4205 capsules must be stored at 2-30 °C (1-30 °C in Korea) in the original container(s), unless being prepared for administration.

All study drugs should be kept in a secure place under appropriate storage conditions. The investigational product label on the pack specifies the appropriate storage.

Drug administration

Patients will receive repeat dosing of AZD4205 at 150 mg or 250 mg once daily. Each cycle of therapy will be approximately 21 day repeated dosing. Patients may continue to receive AZD4205 at the discretion of the investigator until disease progression per Lugano criteria, unacceptable toxicity, discontinuation criteria have met, withdrawal of consent or termination of the study by Sponsor.

AZD4205 capsule(s) can be taken whole with water, with or without regard to food. However, subjects will be required to fast (water only) for at least 8 hours prior to the collection of a serum chemistry sample as per the study plan (see Table 2 and Table 3).

If a patient misses taking a scheduled dose, within a window of 12 hours, it is acceptable to take the dose. If it is more than 12 hours after the dose time, the missed dose should not be taken, and the patient should be instructed to take the next dose at the next scheduled

time. If a patient vomits after taking AZD4205, he/she should not make up for this dose, but should take the next scheduled dose.

5.1.1 Dose escalation and extension part (Part A)

The dose escalation part (Part A) contains two ascending dose cohorts. Each cohort is planned to enroll 10~20 patients with r/r PTCL who will receive AZD4205 at 150 mg or 250 mg once daily dosing. The decision of dose escalation to AZD4205 250 mg level is made by the safety review committee (SRC) based on all the available safety, tolerability and PK data of the starting dose (150 mg). After the RP2D is defined, an extension cohort will enroll ~10-20 patients to evaluate single capsule dosage formulation at RP2D (see Figure 1).

5.1.1.1 Dose escalation cohorts

The first 10 patients will receive AZD4205 at the dose of 150 mg once daily. This dose was defined based on the clinical data from other completed AZD4205 studies, including study DZ2017J0001 (EGFR mutant advanced NSCLC), study DZ2018J0001 (healthy volunteers) and study DZ2019J0002 (healthy volunteers). The 150 mg dose is predicted to be biologically effective for patients with PTCL, especially patients with JAK/STAT pathway aberrations. Once there are 10 evaluable patients who complete the safety assessment in the first repeat dosing cycle in each cohort, a decision will be made by SRC based on safety/tolerability, PK and efficacy data if additional patients need to be enrolled into the same dose cohort or dose escalation to 250 mg.

Patients who discontinue treatment early due to disease progression or withdrawal will be asked to complete all end-of-treatment safety evaluations as described in the protocol. Patients who take less than 80% of planned doses within the first dosing cycle are considered not evaluable and will be replaced, unless the incompletion of dose is caused by dose-limiting toxicity (DLT) like event. Final evaluability should be determined by SRC.

Safety Review Committee (SRC)

The SRC will evaluate the safety, tolerability, efficacy and PK of AZD4205 to decide expansion of a dose cohort or dose escalation to the next level.

The SRC will consist of:

- Sponsor Study Physician
- Global coordinating investigator and national coordinating investigator or their delegate
- Sponsor Safety Physician.

Other principal investigators, Medical Director, Clinical Operation Director, Clinical Pharmacology Scientist, Study Statistician, Patient Safety Scientist, and Study Leader, further internal or external experts may be consulted by the SRC as necessary.

Once there are at least 10 evaluable patients at a dose level, the SRC will review and assess all available safety and efficacy data from the cohort together with available PK to make a

decision on expansion of a dose cohort or dose escalation to the next dose level. Any dose interruptions and reductions will be taken into account.

The decision may be to:

- Expand the cohort to a maximum number of patients.
- Dose escalation to next dose level
- De-escalate the dose to a lower dose level.
- Consider alternative dosing frequencies or intermittent dosing schedules.
- Trigger additional dose cohort(s) based on the safety/tolerability, PK and antitumor efficacy data.

When there are other patients that are ongoing at the time of this review, the SRC may decide to defer their decision until these further patients become evaluable.

Any patient started on treatment in error, as he/she failed to comply with all of the selection criteria but meets the criteria of an evaluable patient, will be reviewed on a case by case basis by the SRC to determine if the patient should be included or excluded for decision.

Definition of DLT-like event

Any toxicity not attributable to the disease or disease-related processes will be considered a DLT-like event if it occurs during Cycle 1 (first 21 days of repeated dosing of AZD4205) in dose escalation cohorts. DLT-like events will be defined as the following:

- > Hematological toxicity including:
 - CTCAE (version 5) Grade 4 or above present for more than 4 days
 - Febrile neutropenia
- > Non-hematologic toxicity including:
 - Grade 3 or 4 non-hematologic toxicity (excluding alopecia), that is dose limiting in the judgment of the investigators and the Medical Monitor/Study Physician
 - Grade 3 or 4 laboratory abnormalities which are not considered clinically significant and which resolve within 48 hours, will not be considered as a DLT
 - An increase in AST or ALT ≥ 3×ULN and total bilirubin ≥ 2×ULN where no other reason other than investigational treatment can be found to explain the combination of increase
 - Confirmed QTc prolongation (> 500 msec absolute or > 60 msec above baseline)
 - Decrease in lung function: either DLCO or FEV1% decrease to ≥ CTCAE Grade 3
 - LVEF decrease to < 40%; or LVEF [40 54%] and LVEF \geq 10% decrease from baseline; or any symptomatic LVEF decrease.
- Any other toxicity that:
 - is greater than baseline, is clinically significant and/or unacceptable, and is judged

to be a DLT-like event by the SRC

- that is a protocol defined stopping criteria (i.e. confirmed pneumonitis or life-threatening arrthymia)
- prevents completion of at least 80% of planned doses

Dose escalation scheme

Once there are 10 evaluable patients in the initial dose cohort (i.e. completing > 80% of the planned dose in Cycle 1, or DLT-like event preventing the dose completion), the SRC will review all available safety/tolerability, PK and efficacy data in 150 mg dose cohort. If \leq 30% of patients have DLT-like event, the dose level of AZD4205 may be escalated to 250 mg once daily. If DLT-like events are observed in > 30% of patients and efficacy signal is observed, it is recommended to continue enrolling another 10 patients in the original dose cohort (150 mg) to further assess the safety, tolerability and anti-tumor efficacy. If > 30% of patients have DLT-like event and no efficacy signal is observed, further enrollment of additional patients would be ceased. In addition, all drug interruptions and dose reductions will be taken into consideration for the decision of dose escalation by SRC.

5.1.1.2 Dose extension cohort

Once the MTD, MAD or RP2D is defined based on safety, tolerability, PK, and efficacy data of dose escalation part, a cohort of around 10~20 patients with r/r PTCL will be enrolled to evaluate single capsule dosage formulation at the selected dose.

5.1.2 Phase 2 dose expansion cohort

Once the RP2D is determined, an additional cohort of patients with r/r PTCL will be enrolled to further assess the efficacy and tolerability of AZD4205. Approximately 100 patients with r/r PTCL are planned to be enrolled, while as the result of this part is planned to support an NDA submission for AZD4205, the sample size will be discussed and agreed with regulatory authorities before initiation of enrollment. Patients will receive AZD4205 treatment until disease progression, unacceptable toxicity, discontinuation criteria have met, withdrawal of consent or termination of the study by Sponsor.

Stopping criteria for dose expansion cohort (Part B)

In Phase 2 dose expansion cohort (Part B), around 100 patients with r/r PTCL are planned to be enrolled continuously and receive AZD4205 at 150 mg once daily. TEAE related discontinuation or death will be continuously monitored. After \geq 20 patients are enrolled and once the rate of TEAE related discontinuation or death reaches \geq 19.7%, an ad-hoc SRC meeting will be triggered to review all available safety, tolerability and efficacy data of Part B. In the case of treatment-related death occurred (\geq 1), the study accrual will be suspended and SRC meeting will be triggered. The decision of SRC may be to:

- Make decisions on the patient recruitment plan, e.g. enrollment suspension and resumption.
- Adjust the risk management plan for the expansion cohort (Part B)
- Re-evaluate the risk-benefit balance

The criteria of 19.7% is calculated based an algorithm close to Bayesian Optimal Interval (BOIN) design (Liu S et al. 2015). We will set our target rate as 15% and un-acceptable rate as 25%. The boundary is calculated similar to λ_d in BOIN design. The un-acceptable rate of 25% is set based on TEAE leading to dose discontinuation rate in pivotal trials of approved drugs for r/r PTCL, which ranges from 19 to 23% (Coiffier B et al, 2012; O'Connor OA et al. 2011; O'Connor OA et al, 2015). While target rate is similar to our current observed TEAE leading to dose discontinuation rate of 13.9% (Data from Part A of DZ2019J0005 study as of September 11, 2020).

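### The Part B safety trigger has no defined denominator or minimum follow-up, yet its 19.7% boundary assumes known outcomes; read as events per enrolled, the rate is understated during accrual and the review tends to come late

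*Protocol*

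**What the plan says.** Under the Part B stopping criteria in Protocol section 5.1.2, about 100 patients "are planned to be enrolled continuously and receive AZD4205 at 150 mg once daily". Discontinuations and deaths are watched continuously. After at least 20 "patients are enrolled and once the rate of TEAE related discontinuation or death reaches" 19.7%, an ad-hoc SRC meeting is called; among other things, the SRC can suspend or resume enrolment. Separately, a single treatment-related death suspends accrual and brings the SRC together.

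On the boundary: "The criteria of 19.7% is calculated based an algorithm close to Bayesian Optimal Interval (BOIN) design", computed in the manner of that design's λ_d, with "target rate as 15% and un-acceptable rate as 25" per cent. The upper value comes from "TEAE leading to dose discontinuation rate in pivotal trials of approved drugs for r/r PTCL, which ranges from 19 to 23" per cent. The 15% is described as close to the 13.9% seen in Part A at a data cut of 11 September 2020.

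The only patient count the rule names is the number enrolled. No denominator, exposure requirement or evaluability window is given for Part B. SAP section 6 plans no interim analysis, and the SAP has no monitoring rule. Part A differs: section 5.1.1.1 counts evaluable patients only (more than 80% of Cycle 1 doses taken, or a DLT-like event that prevented this), and the SRC may wait for further patients to become evaluable.

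**The concern.** A λ_d boundary is a cut-off for a binomial proportion: each counted patient is either an event or a known non-event. Under continuous accrual most counted patients are neither. If the rate is events over patients enrolled, someone dosed last week enters the denominator in full while having had almost no chance to enter the numerator.

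The protocol suggests that events will not all be early. Table 1 reserves permanent discontinuation for the third occurrence of several toxicities, after holds of up to 14 or 21 days. The first on-treatment lung function, LVEF and eye examinations fall at Cycle 3, about six weeks in (section 6.4.5). Treatment may last about two years (section 5.1.4).

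At stake is timing. This is the only rule in the documents that tracks cumulative discontinuation in Part B, and a review that can suspend enrolment helps later patients only if it comes while they are still to be enrolled.

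**Working it through.** **1. The plan's figure.** With φ = 0.15 and φ₂ = 0.25 (section 5.1.2):

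λ_d = ln[(1 − φ)/(1 − φ₂)] / ln[φ₂(1 − φ)/(φ(1 − φ₂))] = ln(0.85/0.75) / ln(0.2125/0.1125) = 0.1252/0.6360 = 0.1968.

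The 19.7% reproduces.

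**2. Benchmark: outcomes known at entry, true rate 25%.** At 20 patients the rule needs 4 events (4/20 = 20%; 3/20 = 15%). P(at least 4 of 20) = 0.775. With continuous looks, simulation gives P(trigger by 40 enrolled) = 0.91 and a median trigger at patient 20. The boundary works as intended when outcomes are known.

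**3. Outcomes still accruing.** The documents give neither accrual speed nor time to event, so these are assumptions: 100 patients enrolled uniformly over 12, 18 or 24 months; exponential time to event with median m of 1.5 or 3 months among patients who will have one; true eventual rate p = 0.25. With T the months of accrual so far and λ = ln 2/m:

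expected crude rate ≈ p × [1 − (1 − e^(−λT))/(λT)].

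- 12-month accrual, m = 3. At 20 enrolled T = 2.4 and λT = 0.555, giving 0.25 × 0.232 = 0.058. At 60, T = 7.2 and λT = 1.664, giving 0.25 × 0.513 = 0.128.
- 24-month accrual, m = 1.5. At 20 enrolled T = 4.8 and λT = 2.218, giving 0.25 × 0.598 = 0.150. At 60, T = 14.4 and λT = 6.654, giving 0.25 × 0.850 = 0.212.

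Simulated means are 0.054 and 0.127 in the first case, 0.145 and 0.208 in the second.

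**4. Chance of a trigger by 60 enrolled at a true 25%** (simulation, checked at every event and enrolment from patient 20). The last column applies the same 19.7% to patients first dosed at least 12 weeks earlier, once 20 such patients exist.

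| Accrual | Median time to event | Events/enrolled | 12-week group |
|---|---|---|---|
| 12 months | 3 months | 0.15 | 0.53 |
| 18 months | 3 months | 0.36 | 0.61 |
| 24 months | 3 months | 0.51 | 0.73 |
| 12 months | 1.5 months | 0.56 | 0.80 |
| 18 months | 1.5 months | 0.72 | 0.84 |
| 24 months | 1.5 months | 0.84 | 0.90 |

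Repeat simulations put the best crude case between 0.77 and 0.84, so the entries are good to several points. The chance of a crude trigger before the 100th patient is about 0.35 to 0.92.

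**5. A second grid.** Accrual of 4, 6 or 10 patients a month and medians of 1, 2 or 4 months give a mean crude rate of 3.8% to 16.9% at patient 20, below 19.7% in all nine cases. P(trigger by 40 enrolled) is 0.02 to 0.79, against 0.91 in step 2. In the mildest case (4 a month, 1-month median) the median trigger is at patient 21 rather than 20, a negligible delay.

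**6. Behaviour of the 12-week addition.** Twelve weeks is 84/30.4375 = 2.76 months. The rule first applies at about 20 + 2.76 × (100/accrual months) enrolled: 43, 35 and 31 for 12, 18 and 24 months. With m = 3, a patient at 12 weeks has passed 1 − 2^(−2.76/3) = 47% of the eventual risk, so some lag stays. Triggering on either rate gives P(trigger by 60) of about 0.5 to 0.9 at a true 25%. At a true 15% it raises that probability from about 0.01-0.25 to 0.12-0.40.

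**The case against.** A reader might infer that the protocol specifies events per enrolled patient. It does not: the 20 enrolled is an activation condition and the denominator is left open. Events per enrolled is the natural reading, but it remains a reading.

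A reader might also infer that the boundary is built wholly from completed-treatment rates. The text does not support that. The 15% leans on an interim 13.9%, which may itself be immature. For the 25%, the protocol says only that the rates come from pivotal trials of approved drugs, and it sets 25% above their 19 to 23% range.

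Three further points limit the effect. The monitored event includes death, whereas both boundary sources are discontinuation only. This offsets the lag in part: at an assumed 30% composite, the mean crude rate at patient 20 is still 7.9% to 20.2% over three scenarios. A treatment-related death has its own, stricter trigger, though it does not cover discontinuations. And reaching 19.7% calls a meeting; it does not stop accrual.

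The size is also assumption-driven. It would be wrong to say that the crude rate stays under the boundary for most of accrual whatever the pace: with 24-month accrual and a 1.5-month median, the mean is 0.196 at 40 enrolled and 0.208 at 60.

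These points limit the claim without removing it. Nothing in section 5.1.2 prevents unobserved follow-up from being counted as event-free, and that error runs in one direction.

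**Conclusion.** The point holds in this form: the 19.7% rule has no defined denominator and no follow-up requirement, and if applied as events over enrolled it understates the eventual rate during accrual and tends to call the SRC late. The direction follows from the structure of the rule. The size rests on the assumed accrual and event timing in the working: at a true 25%, from 0.15 to about 0.84 for a trigger by 60 enrolled, with little delay when accrual is slow and events are early. The documents do not show that a late trigger has happened or will happen. The sponsor should act, because the rule as written weakens a safety trigger and the remedy is cheap. Confidence is medium.

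**What to change.** In section 5.1.2:

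- Define the denominator of the monitored rate.
- Keep 19.7%, the minimum of 20 patients and the SRC actions as they are.
- Add that the ad-hoc SRC meeting is also called when the rate reaches 19.7% among patients with a stated minimum follow-up, once 20 such patients exist. First dose at least 12 weeks before the look is one example; that length is not derived from the documents, and the sponsor should justify its choice.
- State the trigger probabilities at true rates of 15% and 25% under the planned accrual.

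The cost is a few sentences and a second column in the running safety tabulation, with no new data or patients. The addition cannot act at the first look (it starts at about 30 to 45 enrolled) and reduces the lag without removing it. The price is more ad-hoc meetings when the drug is acceptable, as step 6 of the working shows. The boundary is already sensitive under continuous looks: with outcomes known at entry and a true 15%, it fires in about 0.52 of simulated trials.

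The documents do not state current accrual. If it is complete, the same calculation should be used to interpret the monitoring record.

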5.1.3 Dose modifications

5.1.3.1 Toxicity management and dose modifications to AZD4205

If a patient has a treatment emergent adverse event (TEAE) at least possibly related to AZD4205, then dose interruptions/holds with possible modifications as described in Table 1 should be implemented. Deviations from these guidelines may occur based on the clinical judgment of the investigator with notification to the Sponsor. For managing toxicity related to the eye, refer Appendix VII.

Table 1 Dose Interruptions/Modifications for Toxicities Observed in the Study

Category	Toxicities needing immediate interruption	Dose modification plan
	$\mathrm{ANC} < 0.5 \times 10^9/\mathrm{L}$	Immediate interruption of AZD4205. Once toxicity has resolved to recovery to ≤ Grade 2 or baseline within 14 days of onset: Resume at the same dose for the 1st occurrence of the event Resume at the reduced dose for the 2nd occurrence of the event Permanent discontinue for the 3rd occurrence of the event
Hematological	Platelet count $< 25 \times 10^9/L$	Immediate interruption of AZD4205 Once toxicity has resolved to recovery to ≤ Grade 2 or baseline within 21 days of onset: Resume at the same dose for the 1st occurrence of the event Resume at the reduced dose for the 2nd occurrence of the event Permanent discontinue for the 3rd occurrence of the event
toxicity	Grade 3 febrile neutropenia	Immediate interruption of AZD4205 Once toxicity has resolved to recovery to ≤ Grade 2 or baseline within 14 days of onset: Resume at the reduced dose for the 1st occurrence of the event, unless the toxicity can be safely and reliably controlled to ≤ Grade 2 or baseline with appropriate treatment, (dose may restart at 150 mg once daily after reaching an agreement with the sponsor). If the same non-hematological toxicity requiring dose interruption occurs again, AZD4205 should be permanently discontinued.
	Grade 3 thrombocytopenia with significant bleeding Other Grade 4 or unmanageable hematological toxicity(ies)	Permanent discontinuation Immediate interruption of AZD4205

		Once toxicity has resolved to recovery to \leq Grade 2 or baseline within 14 days of onset:
		Resume at the same dose for the 1st occurrence of the event
		 Resume at the reduced dose for the 2nd occurrence of the event
		 Permanent discontinue for the 3rd occurrence of the event
	QTcF > 500 ms absolute or > 60 ms increase from baseline	Permanent discontinuation
	QT prolongation (QTcF > 450 ms) with signs/symptoms of life-threatening arrhythmia	Permanent discontinuation
	Confirmed drug-induced pneumonitis (any grade, see Figure 3)	Permanent discontinuation
	Grade 4 non-hematological toxicity	Permanent discontinuation
		Immediate interruption of AZD4205
Non-		Once toxicity has resolved to recovery to \leq Grade 2 or baseline within 21 days of onset:
hematological	Grade 3 Herpes Zoster	 Resume at the same dose for the 1st occurrence of the event
toxicity		 Resume at the reduced dose for the 2nd occurrence of the event
		 Permanent discontinue for the 3rd occurrence of the event
		Immediate interruption of AZD4205
		Once toxicity has resolved to recovery to \leq Grade 2 or baseline within 14 days of onset:
	Other Grade 3 or unmanageable non-hematological toxicity(ies)	Resume at the reduced dose for the 1st occurrence of the event, unless the toxicity can be safely and reliably controlled to \(\leq \text{Grade 2} \) or baseline
		with appropriate treatment, (toose may restait at 150 mg once daily after reaching an agreement with the sponsor).
		■ If the same non-hematological toxicity requiring dose interruption occurs again, AZD4205 should be permanently discontinued.

The reduced dose level of AZD4205 refers to 75 mg once daily. Patient should discontinue the study treatment, if he/she is already at the reduced dose level (75 mg) and requiring a further dose reduction due to toxicity according to the modification plan (as defined in Table 1).

If medically appropriate, Grade 4 abnormalities of hematology parameters which are considered to be of clinical concern may be repeated/confirmed within 7 days and followed up as appropriate. Supportive care such as transfusion and/or growth factor could be given per institutional guideline.

Supportive care for the management of the toxicities may be given to the patients as required in accordance with local practice/guidelines. Patients should permanently discontinue the study treatment, if the toxicities leading to interruption do not recover to ≤ Grade 2 or baseline within the maximum duration of dose interruption defined in Table 1. Patients with toxicities leading to dose discontinuation should be followed up until Grade 1 or baseline. Deviations from above guidelines may occur based on the clinical judgment of the Investigator with reaching agreement with the Medical Monitor/Sponsor.

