5.2.2 Potential risks

Non-clinical toxicity studies of AZD4205 in rats and dogs and safety pharmacology experiments have been summarized in Section 2.3 of this protocol, which may indicate the potential adverse effects of AZD4205 in human. Further detailed information of non-clinical toxicity findings is available in the Investigator Brochure. The monitoring and management of the potential adverse effects of using AZD4205 is discussed below.

Cardiovascular effects

Patients who have unstable cardiac conditions and risk factors for QT prolongations will be excluded from participation in this study (detailed exclusion criteria are listed in Section 4.2). Concomitant use of regular medications that may prolong the QT interval will be restricted whenever feasible (See Appendix II), but patients may receive any medication that is clinically indicated for the treatment of AEs. Electrolyte and vital sign assessments, including pulse rate and blood pressure, will be monitored regularly throughout the study (See Section 6.1). Twelve lead ECG will be conducted throughout the study to monitor any

change of QT interval. Confirmed QTc prolongation (> 500 msec absolute or > 60 msec above baseline) is the dose interruption criteria (See Section 6.4.3). The investigator or designated physician will review each ECG prior to discharge from the clinic and may refer to a local cardiologist if appropriate for immediate management of the patients. A paper copy should be filed in the patient's medical records. If an abnormal ECG finding at screening or baseline is considered to be clinically significant by the investigator, it should be reported as a concurrent condition. An Echocardiogram or MUGA scan to assess LVEF will be performed at screening prior to first dose of AZD4205 to evaluate any pre-existing cardiac abnormality, followed by Cycle 3 Day 1, and then every 12 weeks, and wherever and whenever necessary as clinically indicated throughout the study. An asymptomatic LVEF decrease to < 40% or LVEF [40-54%] and LVEF decrease ≥ 10% from baseline or any symptomatic LVEF decrease are the dose interruption criteria (See Section 6.4.5 and Appendix VII). Both high sensitive troponin T testing and NT-pro BNP will be performed at screening, baseline and each subsequent cycle.

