After paper ECGs have been recorded, the investigator or designated physician will review each of the ECGs and may refer to a local cardiologist if appropriate. A paper copy should be filed in the patient's medical records. If an abnormal ECG finding at screening or baseline is considered to be clinically significant by the investigator, it should be reported as a concurrent medical history condition. If there is a clinically significant abnormal ECG findings during the treatment period, this should be recorded on the AE CRF, according to standard adverse events collection and reporting processes (see section 6.5.3 and 6.5.4). It is recommended that asymptomatic ECG findings should be adjudicated by an expert reader in case they are reported as AEs with the ECG abnormaity given as explantory information. For all ECGs details of rhythm, PR, R-R, QRS and QT intervals and an overall evaluation will be recorded. All ECGs of patients with any value > 470 ms QTcF are to be sent for immediated review by the study team.

All ECG data will also be collected digitally for each patient and will be transferred electronically for central analysis as described in the study specific ECG manual (if applicable). Heart rate, PR, R-R, QRS and QT intervals will be determined and reviewed by an external cardiologist (if applicable).

Confirmed QTc prolongation (> 500 msec absolute or > 60 msec above baseline) is the dose interruption criteria.

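### Protocol section 5.1.3.1 gives two unranked conditions for departing from Table 1, and the looser one allows dosing past a permanent stop on notification alone; the QTc wording in 5.2.2 and 6.4.3 also needs aligning with Table 1

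*Protocol*

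**What the plan says.** Section 5.1.3.1 of the protocol sets the hold, reduce and stop rules in Table 1. The text introducing the table adds: "Deviations from these guidelines may occur based on the clinical judgment of the investigator with notification to the Sponsor." The paragraph that closes the section, below the table, says: "Deviations from above guidelines may occur based on the clinical judgment of the Investigator with reaching agreement with the Medical Monitor/Sponsor." That same paragraph contains the non-recovery stop ("Patients should permanently discontinue the study treatment, if the toxicities leading to interruption do not recover to" Grade 2 or better, or baseline, within the allowed time). Neither sentence excludes any row of the table, and the notification sentence gives no timing.

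Elsewhere Table 1 asks for sponsor agreement for a smaller step. After a Grade 3 event that has been controlled, the "dose may restart at 150 mg once daily after reaching an agreement with the sponsor". Section 5.3.1 adds no independent stop: it lists adverse events among the situations in which a patient may be taken off drug and points back to Table 1.

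On QT, Table 1 lists "QTcF > 500 ms absolute or > 60 ms increase from baseline" with permanent discontinuation as the plan. Section 5.2.2 labels confirmed prolongation at these limits a dose-interruption criterion and refers to section 6.4.3, which says: "Confirmed QTc prolongation (> 500 msec absolute or > 60 msec above baseline) is the dose interruption criteria." Section 6.4.3 also provides that "All ECGs of patients with any value > 470 ms QTcF are to be sent for immediated review by the study team." Appendix VII asks for a repeat ECG within 5 to 10 minutes when QTcF exceeds 500 ms, and withdrawal if the value is confirmed. It sets no action for a rise above 60 ms alone.

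**The concern.** Both sentences in 5.1.3.1 are permissions. When two permissions cover the same act on different terms and nothing ranks them, the looser one can be relied on. Here the act includes continuing AZD4205 past a row whose plan is permanent discontinuation.

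The exposure is greatest where no other rule repeats the stop: Grade 3 thrombocytopenia accompanied by significant bleeding, Grade 4 non-hematological toxicity not covered by Appendix VII, a QTcF rise above 60 ms, and the stops triggered by recurrence. Some of these need not be serious adverse events. Section 6.5.3 separates severity from seriousness, so a second Grade 3 non-hematological event, or an asymptomatic QTcF rise, may never enter the 24-hour reporting route in section 6.5.4. For such events the wording of 5.1.3.1 is the main control on continued dosing.

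The QTc point is separate and smaller. A reader who starts from the ECG section finds the word interruption and no final action, whereas Table 1 ends treatment. Section 5.3.1 makes that difference matter, because drug that has been permanently discontinued cannot be resumed.

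**Working it through.** The plan states no figure on this point, so there is none to reproduce. The check is a comparison of texts, plus a small piece of arithmetic on the QTcF thresholds.

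**Step 1. The two departure conditions.**

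| | Ahead of Table 1 | Below Table 1 |
|---|---|---|
| Who decides | investigator | investigator |
| Sponsor's part | is notified | agrees (medical monitor or sponsor) |
| Timing | not stated | agreement has to be reached |
| Rows exempted | none | none |

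Obtaining agreement also notifies, so the stricter condition satisfies both sentences. Notification alone satisfies only the sentence ahead of the table. No text says that this is insufficient.

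**Step 2. The QTc statements.**

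| Place | Trigger | Confirmation needed | Final action for a rise above 60 ms |
|---|---|---|---|
| Table 1 | > 500 ms or rise > 60 ms | not mentioned | permanent discontinuation |
| 5.2.2 | same limits | yes | not stated; refers to 6.4.3 |
| 6.4.3 | same limits | yes | not stated; no reference to Table 1 |
| Appendix VII | > 500 ms | yes | none given |

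The places therefore differ in two ways: on the final action, and on whether a single unconfirmed reading is enough.

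**Step 3. Where the other QTcF triggers leave a > 60 ms rise uncovered.** Let b be the baseline QTcF. Assume b ≤ 450 ms. The entry limit in section 4.2 applies to the screening ECG, so carrying it over to the pre-dose baseline is an assumption.

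- Table 1 stop: QTcF > b + 60.
- Study-team review (6.4.3): QTcF > 470.
- Withdrawal if confirmed (Appendix VII): QTcF > 500.

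Withdrawal covers every such rise when b + 60 ≥ 500, that is b ≥ 440. Review covers every such rise when b + 60 ≥ 470, that is b ≥ 410. For 410 ≤ b < 440, values above b + 60 and up to 500 ms get the review but not the withdrawal rule. For b < 410, values in (b + 60, 470] meet the Table 1 stop with neither trigger. The width is 470 − (b + 60) = 410 − b:

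- b = 400: (460, 470], 10 ms
- b = 390: (450, 470], 20 ms
- b = 380: (440, 470], 30 ms

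**Step 4. Does this reach the statistics?** With N = 100, a null ORR of 15%, an alternative of 27% and a two-sided 5% exact test, rejection needs at least 23 responses. The upper-tail alpha is 0.0221 and the power 0.8448, matching the stated 84.5%. The safety boundary is ln[(1 − 0.15)/(1 − 0.25)] / ln[0.25 × 0.85 / (0.15 × 0.75)] = 0.1968, matching the stated 19.7%. Neither calculation uses the departure wording.

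**The case against.** The best defence of the departure wording is that the section should be read whole. The agreement sentence comes last, refers back to what precedes it, and is satisfied together with the notification sentence by seeking agreement. That stands as a description of what a careful site would probably do. A scope reading is also available: notification for holds and modifications, agreement for going past a stop. It is sensible, but the protocol does not say it. The alternative narrow reading, in which the agreement sentence governs only its own paragraph, would leave the Table 1 permanent stops under notification alone. The defence is strongest for the non-recovery stop, which shares a paragraph with the agreement sentence, and for serious events, where section 6.5.4 brings the sponsor in within 24 hours with advice. It is also fair that the permissive verb in 5.3.1 proves little: the same list includes pregnancy, for which section 8.3.1 requires immediate discontinuation.

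On QTc, the defence is that interruption names the trigger and not the outcome. Table 1 heads its whole trigger column in terms of interruption, permanent stops included. Section 6.4.5 calls a symptomatic LVEF decrease an interruption criterion and then orders discontinuation. This largely succeeds. A reader might infer that 5.2.2 and 6.4.3 permit restarting after a > 60 ms rise. They do not say so, and Table 1 is clear. What remains is that, unlike the LVEF text, the QTc text supplies no final action and no reference to Table 1. Appendix VII does not fill the gap: its bar on restarting covers only prolongation with serious arrhythmia.

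The bands in step 3 count two triggers only. Central ECG analysis, described in 6.4.3 (where applicable) and Appendix VII, is a further route to expert review.

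**Conclusion.** The departure point holds: two unranked conditions, one of which, as written, allows dosing past a Table 1 permanent stop on notification alone. It would be too strong to say that the protocol's settled rule is notification, or that sites will use it that way. The documents give no frequency of departures, and the whole section points a careful reader to agreement.

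The QTc point is secondary, a matter of cross-reference and of the word confirmed. The 10, 20 and 30 ms bands rest on the assumed baseline limit of 450 ms. They show where the 470 ms and 500 ms triggers do not apply and do not measure harm, since the documents give no rate of QTcF rises.

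A reader might also infer that the wording distorts the 19.7% safety trigger. At 20 patients, 3/20 = 15% is below it and 4/20 = 20% is above it, so one patient can matter in principle. With no rate to work from, no effect on that trigger is claimed. ORR, alpha and power are unaffected. This is a cheap improvement to the conduct and safety text.

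**What to change.** 1. In the sentence ahead of Table 1, replace notification with *prior agreement of the Medical Monitor/Sponsor*, in line with the sponsor's own closing sentence.
2. Add: *Departures that are more cautious than Table 1 (earlier hold, dose reduction or stop) need notification only.* Without this, a protective step such as resuming at 75 mg where Table 1 allows the same dose would have to wait for agreement.
3. In 5.2.2 and 6.4.3, say that the QTc finding *requires immediate interruption and, once confirmed, permanent discontinuation (Table 1)*.
4. Add *confirmed* to the QTcF row of Table 1, so that all three places agree and a single unconfirmed reading leads to a hold.

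The cost is one phrase, one added sentence and three QTc edits at the next amendment. In conduct, the downside is a short wait for agreement before continuing drug against Table 1. A QTc stop made under the aligned wording would count towards the discontinuation rate compared with 19.7%, but Table 1 already requires that stop.
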